### *TactiFlex PAF IDE*

### *Safety and Effectiveness of TactiFlex Ablation Catheter, Sensor Enabled (TactiFlex SE) for the Treatment of Drug Refractory, Symptomatic, Paroxysmal Atrial Fibrillation*

Version Number

[REDACTED]

Date

May 29, 2020

Planned Number of Sites and Region(s)

Up to 40 sites Worldwide

Clinical Investigation Type

Prospective, non-randomized multi-center clinical investigation. Design includes a main study and a separate substudy. Subjects in the main study are to be treated using the full range of ablation power settings in the IFU. Subjects in the substudy are to be treated in the upper end of the recommended ablation power settings (40-50 Watts).

Sponsor

Abbott

[REDACTED]

CIP Author of Current Version

[REDACTED]

CRD Number

[REDACTED]

[REDACTED]

[REDACTED]

[REDACTED]

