## 3.0 CLINICAL INVESTIGATION DESIGN

This is a prospective, non-randomized, multi-center pivotal clinical trial to evaluate the safety and effectiveness of ablation with the TactiFlex SE catheter for the treatment of PAF compared to pre-determined performance goals. The study design includes a substudy to assure that there will be at least 50 subjects ablated at the high-end of the ablation power setting recommendations in the investigational *Instructions for Use* document. Subjects in the HSP (High Standard Power) substudy are to undergo the same study procedures as subjects in the main study, except that ablation power settings of 40-50 Watts are to be used in the left atrium, unless there is a medical reason to use a lower power. Operators will be assigned to either the main study or the HSP substudy based on the ablation power settings they currently use in their standard practice. Subjects will be enrolled in either the main study or the substudy at the point of consent based on the operator that is expected to perform their ablation procedure. After the substudy has enrolled 50 subjects, or if the Sponsor has provided written permission, HSP operators may transition to the main study and treat main study subjects. No site may enroll more than 10 subjects (20%) in the HSP substudy without Sponsor pre-approval and at least 25 HSP substudy subjects (50%) must be from the United States.

Up to 40 sites worldwide will participate in the TactiFlex PAF IDE clinical study. The TactiFlex IDE Clinical Study will enroll a total of 355 subjects. Fifty (50) subjects will be enrolled in the HSP Substudy and 305 subjects will be enrolled in the Main Study. No center may contribute more than 20% (N=61) of the total number of enrollments in the main study without Sponsor pre-approval. At least 50% (N=153) of the subjects will be from the US.

Subjects will be followed for 12-months after their initial ablation procedure. The primary and secondary endpoints will be evaluated when all subjects have completed their 12-month follow-up visit.

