#### 6.3.3 General Considerations

- Physicians performing ablations must be qualified operators and trained on the study. Each physician who ablates during a particular case needs to be documented on the Procedure CRF. Fellows will not be allowed to perform ablations unless an exception is made by Abbott's Medical Director in writing prior to the fellow performing ablations for this trial. Any fellows granted an

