1.4.3 Additional Data

The following additional data will be collected and reported using only summary statistics and no hypothesis tests with pre-specified criteria will be performed. These Additional Data will be reported separately for main study subjects and HSP substudy subjects. An as treated analysis will be conducted as specified in Section 1.4.4.

1. Proportion of subjects who achieve acute procedural success during the initial ablation procedure, where acute procedural success is defined as confirmation of entrance block in all pulmonary veins after a minimum waiting period of 20-minutes.
2. Proportion of subjects with successful first-pass PV isolation during the initial ablation procedure, defined as confirmation of entrance block in all pulmonary veins following the initial minimum waiting period of 20-minutes.
3. Proportion of subjects who experience any adverse event (AE)
4. Proportion of subjects who experience any serious adverse event (SAE)
5. Proportion of subjects that experience any procedure- and/or ablation catheter-related adverse event (AE) throughout the 12-month follow-up period.
6. Proportion of subjects requiring one or more repeat AF ablations at 12 months following the initial AF ablation procedure.

Statistical Analysis Plan

7. Changes in EQ-5D-5L and AFEQT scores from baseline to follow up at 3, 6, and 12-months after the initial procedure.
8. Procedure data, including but not limited to, ablation data, mapping data, usage of HD Grid, usage of AutoMark, target contact force, power setting data, procedure time, fluoroscopy time, total RF time, time to perform initial PVI, and ablation lesions performed in addition to PVI.
9. Proportion of subjects treated for concomitant typical AFL with the TactiFlex SE catheter
10. Proportion of subjects treated for typical AFL with no recurrent AFL at 3, 6 and 12 months.
11. Proportion of subjects that received CTI ablation with the TactiFlex SE catheter.
12. Proportion of subjects that received CTI ablation that achieved bi-directional block.
13. Evaluation of procedure data to determine target contact force as assessed by AF/AFL/AT recurrence.
14. Evaluation of the relationship between ablation power with time to perform initial PVI.

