2.12 Adjustments for Covariates

Unless otherwise specified, no adjustments for covariates will be made for any of the variables in the analyses.

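### Power follows operator habit, yet the visible plan for the descriptive power analyses takes no account of operator, so operator differences could be mistaken for a power effect

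*Protocol*

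**What the plan says.** **Allocation.** Protocol 3.0, repeated in SAP 1.3, sorts operators by existing practice: "Operators will be assigned to either the main study or the HSP substudy based on the ablation power settings they currently use". Subjects follow: "Subjects will be enrolled in either the main study or the substudy at the point of consent based on the operator" expected to treat them. The sizes are fixed: "Fifty (50) subjects will be enrolled in the HSP Substudy and 305 subjects will be enrolled in the Main Study".

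**Room for power to vary within an operator.** The Protocol's opening design summary says: "Subjects in the main study are to be treated using the full range of ablation power settings in the IFU". Substudy operators may go below 40 W in the left atrium for a medical reason. Once the substudy is full, or with written sponsor permission, "HSP operators may transition to the main study and treat main study subjects".

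**Analyses of power.** SAP 1.4.3 item 14 is "Evaluation of the relationship between ablation power with time to perform initial PVI". SAP 1.4.4 pools main-study and HSP subjects and summarizes results separately by time-averaged power (cut at 40 W) and by the share of left atrial lesions at 40 W or more (cuts at 50% and 25%). All of this is descriptive, without pre-specified hypothesis tests.

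**Adjustment.** SAP 2.12 says that, unless otherwise specified, "no adjustments for covariates will be made for any of the variables in the analyses". SAP 2.10 examines poolability by region and site for the two primary endpoints; its visible text does not mention operator.

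**Data on hand.** Protocol 6.3.3: "Each physician who ablates during a particular case needs to be documented on the Procedure CRF".

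**The concern.** Power was not assigned to subjects independently of who treated them. Operators who habitually use 40-50 W may also differ in speed, experience, lesion strategy and site. Regrouping subjects by achieved power does not undo this, because achieved power still depends largely on the operator.

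Item 14 is the most exposed. Time to complete PVI is plainly open to operator speed, and the item asks about a relationship, not a group description. An association between higher power and shorter PVI time could come from power, from faster operators, or from both. As visibly written, the analysis cannot tell these apart. The as-treated endpoint summaries share the weakness. They matter because secondary objective 1 seeks supporting data on use at 40-50 W, and a reader will naturally set the two columns side by side.

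There is also a precision issue. Subjects treated by one operator tend to resemble each other, so any interval that ignores operator is too narrow.

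**Working it through.** **1. The plan's own figures.** 50 + 305 = 355 subjects. The HSP site cap is 10/50 = 20%, which implies at least 50/10 = 5 sites if no exception is granted. The main-study cap is 61/305 = 20%. All agree. No sample size for a power comparison is visible.

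**2. Inputs not in the documents (assumed).** Operator ICC 0.05 to 0.4; HSP subjects from 5 operators of 10 or 10 operators of 5; 20 to 35 main-study operators; cohort fixed by operator; no true power effect.

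**3. Formula.** With m subjects per operator the design effect is 1 + (m - 1) × ICC, and the effective size is n divided by it. In SD units, the naive variance of a difference in means is 1/50 + 1/305 = 0.0233. The actual variance multiplies each term by its design effect. Coverage of a nominal 95% interval is about 2Φ(1.96/√r) - 1, where r is actual over naive variance.

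**4. Worked case.** ICC 0.1, 5 HSP operators of 10, 20 main-study operators (305/20 = 15.25 each):
- HSP: 1 + 9 × 0.1 = 1.9; 1.9/50 = 0.0380
- Main: 1 + 14.25 × 0.1 = 2.425; 2.425/305 = 0.0080
- r = 0.0460/0.0233 = 1.97; 1.96/√1.97 = 1.40; coverage about 84%

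**5. Simulation** (unequal-variance interval, no power effect, 50/305 split). The lower coverage figure belongs to 5 HSP operators, the higher to 10.

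| ICC | Effective HSP size, 5 × 10 | Effective HSP size, 10 × 5 | Coverage of nominal 95% interval |
|---|---|---|---|
| 0.05 | 50/1.45 = 34.5 | 50/1.2 = 41.7 | about 89-92% |
| 0.1 | 50/1.9 = 26.3 | 50/1.4 = 35.7 | about 84-89% |
| 0.2 | 50/2.8 = 17.9 | 50/1.8 = 27.8 | about 75-84% |
| 0.4 | 50/4.6 = 10.9 | 50/2.6 = 19.2 | about 62-74% |

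A rerun for this write-up agreed to within about two points; at ICC 0, coverage is 95%. For a binary endpoint at an assumed 70% rate, with 5 HSP operators, the Newcombe interval wrongly excludes zero in 15-17% of trials at ICC 0.1 and 25-26% at 0.2. Comparing operator means instead (continuous outcome) brings this back to 5-6%.

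**6. Effect of mixing.** A different set-up has 355 subjects and 40 operators of uneven size, 10 of them high-power. Coverage at ICC 0.1 and 0.2 is about 80% and 70% if power is fixed by operator, 87% and 78% if 10% of cases are done at the operator's other level, and 93% and 91% if 30% are. This set-up puts about 355 × 10/40 = 89 subjects in the high-power group, against a documented HSP cohort of 50.

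**7. What this does not measure.** An unadjusted contrast estimates the power effect plus the mean operator effect in the high-power group minus that in the low-power group. The simulation sets the expected value of that operator gap to zero, so it shows clustering only. If habitual high-power operators are systematically faster, the whole gap is added as bias. The documents give nothing from which to size it.

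**The case against.** The other side has real force, and most of it stands as a limit on the point.

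- **No interval on a power difference is promised.** Results are to be summarized separately. The unequal-variance and Newcombe differences in SAP 2.2.1 and 2.2.2 are for subgroup analyses where specified, and no visible text specifies them for power. The coverage figures are therefore conditional on such an interval being shown. A reader might infer that the SAP declares subjects independent; it says only that the two groups are.
- **A reader might infer that power hardly varies within an operator.** The documents point the other way: main-study operators have the full IFU range, HSP operators may go lower or move over, and the lesion-share cuts presuppose mixed power within a case. Step 6 shows how mixing weakens the clustering problem.
- **A reader might infer that secondary objective 1 asks what power does.** It asks for supporting data on use at 40-50 W. Only item 14 poses a relationship.
- **The within-operator contrast is not clean.** In HSP, lower power is used for a medical reason, which may itself relate to outcome. It should not be the sole basis for every statement.
- **Redaction.** The as-treated population, part of the poolability text, the method appendices and the substudy rationale are blacked out, so absence is shown for the visible text only.

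What the objection does not remove: item 14 relates an exposure largely chosen by the operator to an outcome open to operator speed, and nothing visible separates the two. A descriptive label does not prevent misreading.

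**Conclusion.** The point holds as a moderate one about descriptive analyses. In the visible text, power and operator are confounded in item 14 and in the as-treated power summaries, so these results could be read as a power effect when they partly reflect the operator. The documents do not show that they will be read that way, and no visible text draws a comparative conclusion.

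Should a standard 95% interval for a difference be shown, its coverage at the 50/305 split would fall from about 89-92% at ICC 0.05 to 62-74% at ICC 0.4. This assumes 5 or 10 HSP operators and cohort fixed by operator, and the loss is milder with more mixing. Bias from systematic operator differences would come on top and is not quantified.

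A reader might extend the point to the primary safety and effectiveness tests. It does not reach them: they compare a rate with a performance goal and involve no power contrast.

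**What to change.** **SAP 1.4.4.** For each power group, tabulate the number of operators and sites and how subjects are spread across them. Use operator-clustered intervals for any difference that is reported.

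**SAP 1.4.3, item 14.** Keep the unadjusted summary. Add a linear model of log time to initial PVI with a random intercept for operator, and power split into the operator's mean and the deviation from it. Report both terms. Since several physicians may ablate in one case, define the primary ablating operator from the Procedure CRF.

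**SAP 2.12.** Name this model as an exception to the default.

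**Caveats to state in the SAP.** The within-operator term may be confounded by the medical reasons for using lower power. If power varies too little within operators, the report should say that power and operator cannot be separated. Clustered intervals correct the width but not the bias.

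Extending the model to contact force (item 13) is optional, because operators are not allocated by force.

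**Cost.** SAP wording and one standard mixed model; no new data, since the ablating physicians are already recorded. The downside is wider intervals and a little more analysis.

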## Clinical Investigation Plan

[figure not shown]
[REDACTED] All adverse events (AEs), with logical exceptions, from the point of enrollment through study exit will be documented and reported. A Clinical Event Committee (CEC) will be used to adjudicate all AEs that are determined by the Sponsor to potentially meet the criteria of 1) a serious AE and/or 2) an AE related to the investigational devices or ablation procedure.

The clinical investigation has been designed to involve as little pain, discomfort, fear, and any other foreseeable risk as possible for subjects. Refer to the Risks Analysis section of this clinical investigation plan for details.

### 3.1 Clinical Investigation Procedures and Follow-up Schedule

The visit schedule for subjects is shown in **Figure 5**. Once eligibility is confirmed, the subject will undergo a study ablation procedure for treatment of their PAF condition. A blanking period of 90-days will be employed after the initial ablation procedure, followed by a 9-month evaluation period. The total follow-up period will be for 12 months. Medication adjustments, cardioversions, and one repeat ablation procedure may be performed in the blanking period without being considered a primary effectiveness endpoint failure (repeat ablation for AF must be performed 31-80 days after the initial procedure). Subjects must be off Class I and III antiarrhythmic drugs (AADs) after the blanking period, unless clinically justified. Follow-up assessments will occur either in-person at the clinic or via phone contact after the procedure. The scheduled follow-up visits will occur before the patient leaves the hospital and then at 7-days (phone call), 5-weeks (phone call), 3-months (in-person visit), 6-months (phone call), and 12-months (in-person visit) after the initial procedure. The subject will be exited from the trial after completing their 12-month follow-up visit.

## Clinical Investigation Plan

**Figure 5. Study Flow Diagram**

## Clinical Investigation Plan

### 3.2 Measures Taken to Avoid and Minimize Bias

Multiple measures will be taken to avoid and minimize bias in this clinical investigation. First, TactiFlex PAF IDE is a prospective clinical investigation in which the outcome is unknown at the time of enrollment and all subjects must meet the defined eligibility criteria to minimize selection bias. Next, guidance will be provided to sites regarding data collection for questionnaires and the post-procedure follow-up phone calls to be performed at 7-days, 5-weeks, and 6-months post-procedure. Additionally, case report forms for data collection will be provided to sites, which will minimize inter-observer variability.

Evaluation of primary endpoint data will be performed by an independent core laboratory and Clinical Events Committee (CEC). Collected electrocardiogram (ECG), trans-telephonic monitoring (TTM), and 24-hour Holter data from sites will be evaluated by a physician at a core laboratory to determine AF recurrence for subjects. To ensure consistent monitoring for arrhythmia recurrence across the subject population, it is required (as permitted by local regulations) that either the core lab or site personnel contact the subjects to help them perform each scheduled TTM transmission and verify that the transmission has been received by the core lab.

A CEC made up of physicians who are not investigators in the trial will be used to adjudicate all AEs that are determined by the Sponsor's Safety group to potentially meet the criteria of 1) a serious AE and/or 2) an AE related to the investigational devices or ablation procedure. To minimize bias, only the core lab and the CEC's adjudication of the collected data will be used for the analysis of the primary safety endpoint.

Protocols are also in place to minimize lost to follow-up subjects (**Section 5.5.1**). Sensitivity analyses will be performed demonstrating the impact missing data may have on the trial.

An independent Data Safety Monitoring Board (DSMB) will be established (**Section 10.9.3**) and serve in an advisory role to the Sponsor to ensure safety by reviewing cumulative data from the clinical investigation at prescribed intervals for the purpose of safeguarding the interests of enrolled subjects and those patients yet to be enrolled, as well as the continuing validity and scientific merit of the clinical investigation.

### 3.3 Suspension or Early Termination of the Clinical Investigation

The Sponsor reserves the right to discontinue the clinical investigation at any stage or reduce the follow-up period with suitable written notice to the investigator. Possible reason(s) may include, but are not limited to:

- Unanticipated (serious) adverse device effect (e.g., UADE, USADE) occurs and it presents an unreasonable risk to the participating subjects
- An oversight committee (e.g., Steering Committee, DSMB) makes a recommendation to stop or terminate the clinical investigation (such as higher frequency of anticipated adverse device effects)
- Further product development is cancelled.

Should the clinical investigation be discontinued by the Sponsor, subjects will be followed per routine hospital practice with device-related AEs reported to the Sponsor as per vigilance/commercial reporting requirements. The investigator shall return all clinical investigation materials (including devices) to the

## Clinical Investigation Plan

Sponsor and provide a written statement to the IRB/EC (if applicable). All applicable clinical investigation documents shall be subject to the same retention policy as detailed in **Section 11.5** of the CIP.

An IRB/EC or regulatory authority may suspend or prematurely terminate participation in the clinical investigation at the investigational site(s) for which they are responsible. The investigators will follow the requirements specified in the Clinical Trial Agreement.

If the Sponsor suspends or prematurely terminates the clinical investigation at an individual site in the interest of safety, the Sponsor will inform all other Investigators.

If suspension or premature termination occurs, the Sponsor will remain responsible for providing resources to fulfill the obligations from the CIP and existing agreements for following the subjects enrolled in the clinical investigation, and the Principal Investigator or authorized designee will promptly inform the enrolled subjects at his/her site, if appropriate.

### 4.0 ENDPOINTS

#### 4.1 Primary Endpoints and Rationale

##### 4.1.1 Primary Safety Endpoint

The primary safety endpoint is the rate of device and/or procedure-related serious adverse events with onset within 7-days of any ablation procedure that uses the TactiFlex SE catheter (initial or repeat procedure performed 31-80 days of initial procedure) that are defined below:

- Atrio-esophageal fistula
- Cardiac tamponade/perforation
- Death
- Heart block
- Myocardial infarction
- Pericarditis
- Phrenic nerve injury resulting in diaphragmatic paralysis
- Pulmonary edema
- Pulmonary vein stenosis
- Stroke/cerebrovascular accident
- Thromboembolism
- Transient ischemic attack
- Vagal nerve injury/gastroparesis
- Vascular access complications (including major bleeding events)

. Atrio-esophageal fistula, cardiac tamponade/perforation and pulmonary vein stenosis will be evaluated through 12-months.

. Bleeding is a major complication of AF ablation if it requires and/or is treated with transfusion or results in a 20% or greater fall in hematocrit.

These events must meet the criteria listed in **Appendix II** to be included in the primary endpoint as adjudicated by the Clinical Events Committee (CEC).

The performance goal for the Primary Safety Endpoint for this clinical trial

= 12.9%.

## Clinical Investigation Plan

[REDACTED]

[REDACTED] Additional details are provided in the Statistical Analysis Plan.

### 4.1.1.1 Rationale for Selection of the Primary Safety Endpoint

Peri-procedural serious adverse events (SAEs) that are adjudicated as being related to the procedure and/or the device are being assessed in the primary safety endpoint. The majority of the pre-identified SAEs that require reporting in this study occur within the first 7-days following an ablation procedure. It has become industry standard to report adverse events with onset within the first 7-days of an ablation procedure for AF. However, symptoms of PV stenosis and atrial-esophageal fistula may not be apparent in the acute period following the procedure. Notably, the 2004 FDA Guidance entitled "Clinical Study Designs for Percutaneous Catheter Ablation for Treatment of Atrial Fibrillation", dated January 9, 2004 [32] recommends that PV stenosis be assessed at 3-months and 1-year post-ablation. Additionally, cardiac tamponade/perforation may be related to the device/ procedure even though it may not be discovered within the 7-day post-procedure period. Therefore, symptoms indicative of PV stenosis, atrial-esophageal fistula, and cardiac tamponade/perforation be assessed throughout the clinical investigation and appropriate follow-up testing be conducted as clinically indicated.

